 Yale Students	 Females of childbearing potential	

NOTE: Is this research proposal designed to enroll children who are wards of the state as potential subjects?

Yes No

6. **Inclusion/Exclusion Criteria:** What are the criteria used to determine subject inclusion or exclusion?

Inclusion Criteria:

- (1) 18 or older
- (2) English literate
- (3) Smoke at least 5 cigarettes per day for the past 6 months
- (4) Expired breath carbon monoxide level \geq 6ppm at baseline or detected urine cotinine level with NicAlert test strip
- (5) Report currently smoking menthol cigarettes

Exclusion Criteria:

- (1) Seeking smoking cessation
- (2) Currently using any stop smoking treatments
- (3) History of serious psychiatric condition (i.e., bipolar disorder, schizophrenia)
- (4) Current uncontrolled medical condition
- (5) Current use of other substances (excluding nicotine and caffeine) or a positive urine toxicology screen
- (6) Living with a menthol smoker (to limit access to menthol cigarettes during the non-menthol phase of the trial)
- (7) Female participants will be excluded if they are currently pregnant or breastfeeding or report an unwillingness to use effective birth control for the duration of the study

7. How will **eligibility** be determined, and by whom? [Write here](#)

Interested participants will call our office and will be provided with verbal information about the project. Interested participants will be initially screened by telephone and will provide their name and contact information and provide answers to short screening questions to assess age, smoking status, menthol preference, and to ensure they are not currently seeking smoking cessation treatment. Participants who meet initial eligibility screening will be invited to complete an intake session. At the intake session, participants will complete an informed consent form. Following this, a research assistant will obtain medical and substance use histories, urine drug and pregnancy tests, and breath CO levels. If study criteria are met, the participant will be scheduled for the subsequent sessions.

8. **Minimizing Risks:** Describe the manner in which the above-mentioned risks will be minimized.

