The principal investigator is responsible for monitoring the data, assuring protocol compliance, and conducting the safety reviews at the specified frequency monthly. During the review process the principal investigator will evaluate whether the study should continue unchanged, require modification/amendment, or close to enrollment. The principal investigator and the Institutional Review Board (IRB) have the authority to stop or suspend the study or require modifications.

- ii. What will the multi-site process be for protocol modifications? N/A this is a single-site study

9. **Statistical Considerations:** Describe the statistical analyses that support the study design.

Data analyses will be conducted with SPSS software. Effect size estimates with 95% confidence intervals will be constructed for each aim to inform future studies. The primary statistical analyses will use within-person repeated measures to test for differences in smoking behavior (e.g., number of cigarettes per day, nicotine dependence) in menthol versus non-menthol phases.

Justification for sample size: Estimation of sample size (n=30) is based on achieving a clinically meaningful precision in effect size estimates for the primary outcome of interest. A power analysis based on $\alpha=.05$ and $\beta=.80$ suggests a sample size of 30 subjects is sufficiently powered to detect medium or large effects ($d>.50$) within-person. Although we will be unable to detect smaller effects, this sample size is reasonable for a pilot study, and data will be used to test the feasibility of the paradigm and adherence monitoring methodology and to estimate effect sizes to inform the optimal sample size for a larger follow-up study.

Data Monitoring: Procedures for data collection, data management, monitoring of data quality and data analysis have been developed and refined in our previous tobacco studies. An experienced data analyst and the PI will supervise these procedures which include use of a computerized database to monitor research activities, screening and enrollment, compliance with protocol, completion of scheduled assessments, and data retrieval. Data quality will be ensured by: 1) extensive training/supervision of research staff in data collection; 2) preliminary review of all assessment instruments prior to data entry and checks for completeness and coding errors; 3) double data entry of written assessment instruments; 4) error-checking statistical programs.

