SECTION II: RESEARCH INVOLVING DRUGS, BIOLOGICS, RADIOTRACERS, PLACEBOS AND DEVICES

If this section (or one of its parts, A or B) is not applicable, check off N/A and delete the rest of the section.

A. RADIOTRACERS

N/A

1. Name of the radiotracer: *Write here*

2. Is the radiotracer FDA approved? YES NO

If NO, an FDA issued IND is required for the investigational use unless RDRC assumes oversight.

3. Check one: IND# *Write here* or RDRC oversight (RDRC approval will be required prior to use)

B. DRUGS/BIOLOGICS

N/A

B. DEVICES

N/A

a)

SECTION III: RECRUITMENT/CONSENT AND ASSENT PROCEDURES

1. Targeted Enrollment: Give the number of subjects:

- Targeted for enrollment at Yale for this protocol: 30
- If this is a multi-site study, give the total number of subjects targeted across all sites: N/A

2. Indicate recruitment methods below. Attach copies of any recruitment materials that will be used.

 Flyers	 Internet/web postings	 Radio
 Posters	 Mass email solicitation	 Telephone
 Letter	 Departmental/Center website	 Television
 Medical record review*	 Departmental/Center research boards	 Newspaper
 Departmental/Center newsletters	 Web-based clinical trial registries	 Clinicaltrials.gov
 YCCI Recruitment database	 Social Media (Twitter/Facebook):	
 Other:		

* Requests for medical records should be made through JDAT as described at
<http://medicine.yale.edu/ycci/oncore/availableservices/datarequests/datarequests.aspx>

3. Recruitment Procedures:

- Describe how potential subjects will be identified. Potential subjects will be recruited through methods previously used by our team and found to be effective in recruiting smokers. Recruitment methods include flyers, online advertisements (e.g., Facebook, Craigslist), on public boards in New Haven, and by word of mouth. We will provide a \$25 referral bonus to any current or previous participants if they refer someone who is eligible for the study. We

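### The enrolment target equals the n of the power statement, with no allowance for participants lacking both phases; a two-sided paired t-test at n = 30 already falls short of 80% power at d = .50, and any loss widens the gap

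*Combined protocol and SAP*

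**What the plan says.** The sample-size paragraph of Section I, item 9 (Statistical Considerations) takes alpha .05 and a value of .80 and "suggests a sample size of 30 subjects is sufficiently powered to detect medium or large effects", defined there as within-person d above .50. The contrast is between smoking behaviour "in menthol versus non-menthol phases". The same paragraph also rests the n on the precision of effect-size estimates, concedes that smaller effects will be missed, and calls the size reasonable for a pilot.

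Section III, item 1 then gives: "Targeted for enrollment at Yale for this protocol: 30". The statement of purpose and the research-plan overview repeat 30.

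On the order of events, Section I, item 7 states: "At the intake session, participants will complete an informed consent form". It continues: "Following this, a research assistant will obtain medical and substance use histories, urine drug and pregnancy tests, and breath CO levels". Only people who then meet the criteria are scheduled for further sessions. Section I, item 8 provides for withdrawal by the investigator, and Section III, item 6 lets participants withdraw consent at any time. No section gives a loss rate, an inflation of the target, a replacement rule or a missing-data method, and none defines what counts as enrolled.

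**The concern.** In a within-person comparison of two phases, the n in a simple paired power calculation is the number of people with data in both. Here that n and the recruitment target are the same number, so the stated sensitivity allows for no incomplete participants. Someone who leaves before giving any Phase II data contributes no contrast. If the 30 counts signed consents, so does someone who consents and then fails the drug, pregnancy or CO test.

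At stake is whether the sensitivity printed in the protocol is the one the study can deliver. The results are meant to guide the size of a larger follow-up study, so a reader interpreting a null result needs to know which effects this study could have detected.

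**Working it through.** **Inputs.** From Section I, item 9: alpha .05, n = 30, d = .50 as the boundary of the claim. The .80 is labelled beta; I read it as power. From Section III, item 1: target 30. Not in the documents and therefore assumed: d is the mean within-person difference divided by the standard deviation of the differences; losses of 10%, 20% or 30% of 30 leave no complete pair. Sidedness is not stated, so both versions are shown.

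**Step 1: reproduce the plan's figure.** The normal approximation for a paired comparison is n = ((z for alpha + z for power) / d)².
- Two-sided: ((1.960 + 0.842) / 0.50)² = 31.4, rounded up to 32. Power at 30 is Φ(0.50 × √30 − 1.960) = Φ(0.779) = 78.2%.
- One-sided: ((1.645 + 0.842) / 0.50)² = 24.7, rounded up to 25. Power at 30 is Φ(2.739 − 1.645) = 86.3%.

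The plan's 30 is close to the two-sided normal approximation, with nothing in reserve.

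**Step 2: exact paired t-test.** Power is the probability that a noncentral t variable with n − 1 degrees of freedom and noncentrality d√n exceeds the critical value (the opposite tail is negligible). For n = 30, two-sided, the critical value is 2.045 and the noncentrality is 0.50 × √30 = 2.739, giving 75.4%. Power at d = .50 first reaches 80% with 34 pairs (33 give 79.5%, 34 give 80.8%).

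**Step 3: effect of loss.** Pairs = 30 × (1 − loss).

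| Assumed loss | Complete pairs | Two-sided power at d = .50 | d at 80% power, two-sided | One-sided power at d = .50 | d at 80% power, one-sided |
|---|---|---|---|---|---|
| 0% | 30 | 75.4% | .53 | 84.8% | .46 |
| 10% | 27 | 70.6% | .56 | 81.2% | .49 |
| 20% | 24 | 65.0% | .60 | 76.8% | .52 |
| 30% | 21 | 58.7% | .64 | 71.5% | .56 |

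**Step 4: split the gap.** Two-sided, the move from .50 to .53 is present with no loss at all. Loss adds .56 − .53 = .03 at 10% and .60 − .53 = .07 at 20%.

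**Step 5: precision, the plan's other basis.** With standard error √((1 + d²/2) / n) at d = .50, the 95% half-width is 1.96 × √(1.125 / n): about .38 at 30 pairs, .40 at 27 and .42 at 24.

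**The case against.** The strongest reply is that this is a pilot. Its n is justified first by precision, it admits that small effects will be missed, and the interval half-width moves only from .38 to .42 if 24 pairs remain instead of 30. That stands, and it is why no larger sample is asked for. It does not remove the power claim, which is explicit and separate.

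The one-sided case also has force. The Aim 1 hypotheses are directional, and a one-sided test keeps 80% power at d = .50 with 27 pairs. Against that, the analysis is described as testing for differences and is paired with 95% confidence intervals, which fits a two-sided .05 test better. The plan should say which is meant.

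A reader might go further and infer that the analysed number is bound to fall below 30. The documents do not support this:
- The 30 is a target; no section calls it a ceiling.
- Failing the tests after consent lowers n only if the 30 counts consents. The research plan has eligible participants begin monitoring, so counting those who start is at least as natural a reading.
- Smoking is recorded daily and Phase II has visits on days 14 and 21, so someone who leaves partway through Phase II can still supply a pair.
- Retention is supported by visits at convenient places, back-up contacts and payments of up to $300. Withdrawal for deterioration is described as very rare.

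A reader might also charge the whole shortfall to attrition. Step 4 shows that part of it exists with all 30 complete.

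**Conclusion.** The point holds as an unsupported sensitivity statement with no allowance for loss. Under a two-sided paired t-test the claim is missed modestly with full data: 75.4% power at d = .50, with 80% reached at d = .53. Each lost pair widens the gap, to d = .56 at an assumed 10% loss and .60 at 20%. The loss rates are mine, and the result also rests on reading the printed beta as power and d as standardised by the differences. Under a one-sided test the claim holds with 30 or 27 pairs and fails at 24. The documents do not establish that losses will occur, or at what rate; they establish that losses are foreseen and not allowed for. The consequence is moderate, and wording alone can correct it.

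**What to change.** Keep the target at 30.

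- **Section I, item 9:** state that the test is two-sided and replace the sensitivity claim with wording such as: with 30 complete pairs, d of about .53 is detectable with 80% power, rising to about .56 to .60 if 24 to 27 participants provide data in both phases. Label the 24 to 27 as an assumed range, or replace it with a range from the team's own experience. If a one-sided test is intended, say so and use the one-sided figures. Correct the label on the .80 in the same edit.
- **Section III, item 1:** state whether the 30 counts signed consents or participants who start Phase I. If it counts consents, failures on the intake tests belong in the assumed loss.

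The cost is wording in two places and a slightly less favourable detectable effect. Holding 80% power at d = .50 two-sided would need 34 pairs, or 34 / 0.9 = 37.8, so 38 enrolled at 10% loss, and 34 / 0.8 = 42.5, so 43 at 20%. A pilot aimed at estimation does not require that increase.
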